#### 5.5. Pooling of Centers

No pooling of study centers is planned.

This document is confidential.

## 6. Demographic, Other Baseline Characteristics and Medication

### 6.1. Participant Disposition and Premature Discontinuations

The number and percent of participants will be summarized by treatment group (if applicable) and overall for:

- The Screened Population
- Reason for Screen Failures
- Single-blind Run-in Population
- Reason for Run-in Failures
- ITT Population
- Safety Population
- PK Population
- Evaluable Population
- Participants who completed the study treatment
- Reasons for the early discontinuation of study treatment
- Participants who completed the study
- Reasons for the early discontinuation of study

The treatment and study completion status as well as reason for any premature discontinuations will be listed. A listing for eligibility will be provided.

### 6.2. Demographic and Other Baseline Characteristics

Demographic parameters (eg, age, sex, race, ethnicity, weight, height, and body mass index [BMI, defined as weight in kg divided by height in meters squared], SCD genotype) will be summarized by treatment group for the Safety, ITT, and Evaluable Populations. In addition to the above demographic parameters, smoking status will be listed.

### 6.3. Sickle Cell Disease (SCD) History

SCD history will be listed and summarized by treatment group for the Safety Population. SCD history parameters include the time since SCD diagnosis (years), the type of SCD, number of vaso-occlusive crisis (VOCs) in the 12 months prior to the Screening Visit, the number of events (as defined in Eligibility Inclusion Criterion #6) requiring presentation to acute care clinic, the number of such events resulting in hospitalization, and the duration of current SCD treatment (months).

### 6.4. Medical History

Medical history data will be coded using the Medical Dictionary for Regulatory Activities (MedDRA Version 20.0) or later.

This document is confidential.

The number and percentage of participants with medical histories in each system organ class (SOC) and preferred term (PT) will be summarized by treatment group for the Safety Population. The medical history summary table will be sorted by descending overall total of SOC and PT.

Medical history data will also be listed.

## 6.5. Medication and Procedure

Prior medications/procedures will be defined as medicines/procedures started or stopped prior to the date of first dose of double-blind study drug. Concomitant medications and procedures will be defined as medications/procedures started, continued, or stopped on or after the date of first dose of double-blind study drug. Any medication/procedure started after the date of last dose of study drug will not be considered concomitant for the purposes of analysis.

Medications will be coded according to Anatomical Therapeutic Chemical (ATC) class using the World Health Organization (WHO) Drug Dictionary, Version 201706 DDE (Enhanced) B2 or newer.

Both prior and concomitant medication use will be summarized separately by the number and percentage of participants receiving medication in each ATC level 4 and PT for each treatment group based on the ITT Population. Multiple medications used by a participant in the same ATC class or PT will only be counted once for each corresponding category. Listings for medications and procedures will also be produced and will include medications and procedures reported through the Follow-up Visit.

## 6.6. eDiary Compliance

The eDiary compliance will be calculated for each participant in the Safety Population and summarized by treatment group for the baseline (single blind run-in) and double-blind treatment periods, and weekly. A complete eDiary is defined as having responses to each of the daily eDiary questions.

$$eDiary\ Compliance = 100 \times \frac{Number\ of\ Complete\ eDiary\ Days}{Number\ of\ Expected\ eDiary\ Days}$$

The eDiary compliance will be summarized as outlined in Table 6.

Table 6. eDiary Compliance

Parameter	Description	Variable Type
eDiary Compliance Baseline Double-blind Treatment Period --Week 1 --Week 2 --: --: --Week 12 Overall	Percent of completed eDiary days relative to number of days in reporting interval	Continuous
≥80% Compliance	Number of participants with ≥80% of completed eDiary days	Categorical

This document is confidential.

## 7. Safety Analysis

All safety analyses will be performed using the Safety Population. Safety will be assessed on the basis of AE, clinical laboratory data, vital signs, ECG, physical examinations.

The safety endpoints utilized to access the primary objective of the study, safety and tolerability, are defined in [Section 3.1](#).

### 7.1. Study Drug Exposure and Compliance

Exposure to study drug, calculated as the number of days from the first dose taken post-randomization to the date of the last dose taken, inclusive, will be summarized as both categorical variable (based on different lengths) and numeric variable, by treatment group for the Safety Population. Patient years (defined as total treatment duration in days for a specific treatment group divided by 365.25) will be also derived for participants by treatment group.

The total number of tablets taken between specified visits and overall for the entire study will be calculated for each participant. Treatment compliance will be based on the number of tablets expected to be taken.

$$\text{Compliance (\%)} = 100 \times \frac{\text{Number of Tablets Taken}}{\text{Number of Tablets Expected to be Taken}}$$

The number of tablets taken will be calculated as (total number dispensed – total number lost – total number returned). If the number of tablets lost is missing or unknown, the number lost will be estimated as zero. Compliance will not be calculated if dispensed number or returned number is missing.

Percent compliance for study drug will be summarized by treatment group for each scheduled visit and overall for the Safety Population. Compliance rates will also be categorized as ' $<80\%$ ', ' $80\%-120\%$ ', and ' $>120\%$ ', and summarized by treatment group.

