3.5.5 Treatment Compliance

The appropriate amount of study drug will be dispensed to patients in prelabeled bottles. Patients will be asked to return all bottles (including unused tablets) at each subsequent study visit until the end of the Treatment Period.

Treatment compliance will be based on tablet counts during the Treatment Period.

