5.6 DRUG EXPOSURE AND COMPLIANCE

Exposure to double-blind study drug, calculated as the number of days from the first dose taken to the date of the last dose taken, inclusive, will be summarized by treatment arm for the Safety Population. The total number of doses taken between specified visits and overall for the entire study will be calculated for each subject. Compliance will be based on the number of doses expected to be taken. Percent compliance for double-blind study medication will be summarized by treatment arm and overall for each scheduled visit and overall for the ITT Population.

Compliance rates will also be categorized as missing, <80%, $\geq 80\%$ and $\leq 120\%$, and $>120\%$ and summarized by treatment arm.

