### 3.2. Brief Description

This Phase 2, multicenter, randomized, double-blind, placebo-controlled, parallel-group study with a 2-week single-blind Run-in Period will evaluate the safety and pharmacodynamics (PD) of oral olinciguat compared with placebo when administered QD for approximately 12 weeks in participants with SCD.

At the Screening Visit, participants will undergo preliminary procedures to determine their initial eligibility. At the Run-in Visit (which will occur at least 3 calendar days after the Screening Visit), eligible participants will then begin 14 to 17 days of single-blind placebo dosing and will begin recording their daily and weekly symptom assessments in an electronic diary (eDiary).

On Day 1 of the Treatment Period, participants who continue to be eligible will be randomized to double-blind study drug (QD olinciguat or placebo). Note that participants enrolled under protocol Amendment 3 or earlier were randomized differently than those randomized under Amendment 4 and later, as described below.

- Under Amendment 3 or earlier: Participants were randomly assigned in a 1:1:1:1 ratio to placebo, 2 mg olinciguat, 4 mg olinciguat, or 6 mg olinciguat (see [Table 3](#))
- Under Amendment 4 and later: Participants were randomly assigned in a 3:1 ratio to 18 mg olinciguat or placebo (see [Table 4](#))

On Day 1 and for each up-titration visit, participants must remain in the clinic at least 6 hours postdose and will be allowed to leave thereafter at the Investigator's discretion.

At all scheduled study visits, participants will undergo safety, efficacy, and PK assessments and, as applicable, will take the relevant study drug dose and will be issued study drug supply for subsequent at-home QD dosing. In addition, participants will receive scheduled phone calls in between the scheduled visits to monitor TEAEs and concomitant medications and procedures. Throughout the Treatment Period, participants will continue completing the patient-reported outcome (PRO) questionnaires each day in their eDiary.

Beginning in March 2020, remote visits via phone call have been allowed to accommodate the impact of COVID-19 on study visits and participants' safety. The phone visits, when necessary, have been utilized to collect adverse event, concomitant medication, select vital sign timepoints, uptritration eligibility, and other relevant data.

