### **4.7. Protocol Deviations**

Protocol deviations and major protocol deviations will be identified and documented based on a review of protocol deviations before database lock and treatment unblinding and will be used to define the Evaluable Population. The categories of major protocol deviations to be reviewed include, but are not limited to, participants who:

- Did not meet key inclusion/exclusion criteria in the judgement of the evaluability committee.
- Received disallowed concomitant medication that could meaningfully impact results.
- Had overall treatment compliance rate <80% or >120% (including Single-blind Run-in Period and Double-blind Treatment Period).

This document is confidential.

In addition, the sub-categories 'Related to COVID-19' and 'Unrelated to COVID-19' will be collected to assess the impact of COVID-19 on the protocol deviation data.

The number and percentage of participants with major protocol deviations will be summarized by type of deviation and relationship to COVID-19 and by treatment arm for the ITT Population. All protocol deviations will be presented in a data listing.

This document is confidential.

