## 5. General Aspects for Statistical Analysis

### 5.1. General Methods

All applicable data will be summarized by randomized treatment arm, unless specified otherwise. For summary tables, unless otherwise noted, participants who were randomized to placebo will be summarized as:

- 1) PBO1: participants who were randomized to placebo under Protocol Amendment 3 or earlier,
- 2) PBO2: participants who were randomized to placebo under Protocol Amendment 4 or later, and
- 3) Overall: participants who were randomized to placebo under any version of the protocol.

The participants who were randomized to olinciguat dosing regimens will be summarized as:

- 1) 2 mg: participants who were randomized to 2 mg olinciguat dosing regimen under Protocol Amendment 3 or earlier,
- 2) 4 mg: participants who were randomized to 4 mg olinciguat dosing regimen under Protocol Amendment 3 or earlier,
- 3) 6 mg: participants who were randomized to 6 mg olinciguat dosing regimen under Protocol Amendment 3 or earlier, and
- 4) 18 mg: participants who were randomized to 18 mg olinciguat dosing regimen under Protocol Amendment 4 or later

For safety analysis, the data will be summarized by treatment arm actually received.

In addition, data will be summarized by scheduled visit and/or time-point where appropriate. Unscheduled or repeat assessments will not be included in summary tables, but will be included in listings.

Continuous variables will be summarized using descriptive statistics, including the number of observations (n), mean, standard deviation (SD), median, minimum, maximum and interquartile range (IQR). Categorical variables will be summarized using frequencies and percentages. Unless otherwise specified, percentages will be based on the total number of non-missing values.

Unless otherwise specified, all confidence intervals (CIs) will be 2-sided with a confidence level of 95%. No adjustments will be made for multiplicity.

All statistical analyses will be performed using SAS Version 9.4 or later for Windows.

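### The 80–120% compliance rule for the Evaluable Population counts pre-randomization placebo tablets and gives no result for patients without a return count, and neither change is recorded in SAP Section 11

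*SAP*

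**What the plan says.** **Period.** Protocol 3.5.5: "Treatment compliance will be based on tablet counts during the Treatment Period". Protocol 5.6 summarizes percent compliance for double-blind medication, and the matching deviation rule in Protocol 5.8 does not mention the run-in. SAP 4.7 keeps the 80% and 120% limits but adds "including Single-blind Run-in Period and Double-blind Treatment Period". Under SAP 4.6 a major deviation removes a patient from the Evaluable Population. SAP 8 uses that population for every PD and PRO analysis, alongside the Safety Population (PD) or the ITT Population (PRO).

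**Missing counts.** Protocol 5.6 names a missing category first: "Compliance rates will also be categorized as missing, <80" percent, followed by the in-range and above-range bands. SAP 7.1 keeps only the three numeric bands and states "Compliance will not be calculated if dispensed number or returned number is missing".

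**Denominator.** SAP 5.1 says that, by default, "percentages will be based on the total number of non-missing values". SAP 13.2.5.2 sets the default as the number of participants in the analysis set.

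**Record of changes.** SAP Section 2 requires changes from the protocol's planned analyses to be documented in Section 11. Section 11 lists one change, on work and school absences.

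**The concern.** The Evaluable Population is meant to hold patients who took their randomized treatment adequately. During the run-in everyone takes placebo, so those tablets say nothing about exposure to randomized drug. Counting them lets behaviour before randomization move a patient across the 80% line in either direction. The run-in also carries different weight in the two cohorts, because Amendment 3 used far fewer double-blind tablets.

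The second problem is silence. A patient with no return count has no compliance value, so neither limit can be breached and no row of the compliance table shows that patient. Read literally, one missing return could also leave the overall figure uncalculated. A reader of the report could not tell how many patients had unknown adherence, or whether the Evaluable Population includes them.

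**Working it through.** The documents give no computed figure on this point, so there is none to reproduce. The inputs below come from SAP Tables 2 to 4 and an 85-day schedule.

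**Expected tablets**
- Run-in: 1 tablet a day for 14 to 17 days, so R = 14 to 17.
- Amendment 4 onward: 7×2 + 21×4 + 57×6 = 14 + 84 + 342, so T = 440.
- Amendment 3: 7×1 + 78×2, so T = 163.

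The run-in share of the pooled total is 14/454 = 3.1% to 17/457 = 3.7% under Amendment 4 onward, and 14/177 = 7.9% to 17/180 = 9.4% under Amendment 3.

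**Double-blind compliance implied by a pooled 80%**

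Let d be double-blind tablets taken and r run-in tablets taken. The pooled rule (d + r)/(T + R) ≥ 0.8 is the same as d/T ≥ [0.8(T + R) − r]/T.

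| Cohort, run-in length | Run-in fully taken | 10/14 of run-in taken | None taken |
|---|---|---|---|
| Amendment 4+, 14 days | (363.2 − 14)/440 = 79.4% | 80.3% | 363.2/440 = 82.5% |
| Amendment 4+, 17 days | (365.6 − 17)/440 = 79.2% | 80.3% | 365.6/440 = 83.1% |
| Amendment 3, 14 days | (141.6 − 14)/163 = 78.3% | 80.7% | 141.6/163 = 86.9% |
| Amendment 3, 17 days | (144 − 17)/163 = 77.9% | 80.9% | 144/163 = 88.3% |

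The last column is an outer limit, because the first run-in dose is taken in the clinic. With only that tablet taken in a 17-day run-in, the limits are (365.6 − 1)/440 = 82.9% and (144 − 1)/163 = 87.7%.

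**Two Amendment 3 patients, 14-day run-in**
- Takes 128 of 163 double-blind tablets (78.5%) and all 14 run-in tablets: 142/177 = 80.2%, so no deviation.
- Takes 135 of 163 (82.8%) and 5 run-in tablets: 140/177 = 79.1%, so a major deviation.

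The less adherent patient on randomized drug is kept and the more adherent one is removed.

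**How many patients could move**

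A simulation of 50,000 patients per setting assumed independent missed days at the same rate in both periods, with rates of 10% to 30%. Pooling changed the 80% classification most often at a 20% miss rate: about 3% of patients under Amendment 4 onward and 6.3% under Amendment 3. At 10% the figures were 0.03% and 0.2%. If every patient had the 20% rate, that would be 0.0295×48 = 1.4 and 0.0629×40 = 2.5 patients.

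**Missing counts and the denominator**

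As an illustration, take 36 patients on 18 mg (3:1 of about 48) and assume 4 with known compliance below 80%.

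| Missing | Non-missing denominator | N = 36 | If all missing were below 80% |
|---|---|---|---|
| 2 | 4/34 = 11.8% | 11.1% | 6/36 = 16.7% |
| 4 | 4/32 = 12.5% | 11.1% | 8/36 = 22.2% |
| 6 | 4/30 = 13.3% | 11.1% | 10/36 = 27.8% |

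The two denominator rules give different tables, and without a missing row neither shows the uncertainty in the last column.

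**The case against.** Several points on the other side are sound.

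- SAP Section 2 says the SAP supersedes the protocol's statistics. It does, but the same section requires changes to be identified, and these are not.
- Checking adherence is a stated purpose of the run-in (Protocol 3.2). That supports reporting run-in compliance. It does not support using it to judge exposure to randomized drug.
- The effect of pooling is small under Amendment 4 onward when run-in dosing is good: less than one percentage point. This stands and limits the size of the point.
- Every analysis that uses the Evaluable Population is exploratory and is also run in the Safety or ITT Population. This stands.

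A reader might also infer more than the documents support:

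- *Counting tablets is itself an undeclared error.* Protocol 5.6 says "Compliance will be based on the number of doses expected to be taken", but Protocol 3.5.5 and the Schedule of Events use tablet counts, so the protocol disagrees with itself. In the 18 mg arm every active tablet is 3 mg, so tablet compliance equals the share of prescribed drug taken, which is a defensible measure for PD work.
- *A patient could skip the whole run-in and Days 1–21 and still pass.* The first run-in, Day 1 and Week 1 doses are taken in the clinic, so this cannot happen as stated. Crediting those 7 tablets gives 377/454 = 83.0% of tablets against 67/99 = 67.7% of days. A gap remains, but only for an extreme, clustered pattern.
- *Non-returners automatically stay Evaluable.* The pre-lock deviation list is not exhaustive, and SAP 4.6 excludes olinciguat patients whose concentrations are consistently below quantification. Either may catch some. Neither is a rule for missing counts, and the concentration check cannot detect placebo non-takers.
- *Reported adherence is inflated, especially after remote visits began.* SAP 3.2 says "Beginning in March 2020, remote visits via phone call have been allowed", but no document shows that counts went missing as a result or that non-returners took less drug.
- *SAP 7.1 itself pools the run-in.* It says "The total number of tablets taken between specified visits and overall for the entire study will be calculated for each participant", which is loose, but Protocol 5.6 uses the same scope for doses. Only SAP 4.7 names the run-in.

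**Conclusion.** The point holds in a limited form. SAP 4.7 departs from Protocol 3.5.5 and 5.6 by counting run-in placebo. SAP 7.1 departs from Protocol 5.6 by dropping the missing category. Section 11 records neither, contrary to SAP Section 2. Patients near 80% can be misclassified; most patients will not be. Patients without a return count are not covered by the criterion at all, and the percentage denominator is contradictory.

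The cut-off ranges assume the full 85-day schedule with complete titration. SAP 7.1 does not say how expected tablets are set after a missed uptitration or a dose reduction. If they follow the dose actually prescribed, T is smaller and the run-in weighs more. The simulated percentages rest on assumed miss rates, and the missing-count table is illustrative.

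The point affects the compliance table and the Evaluable analyses. It does not affect the primary TEAE analysis, which uses the Safety Population. It should be corrected, but it does not threaten the trial's main conclusion.

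**What to change.** Before database lock and unblinding:

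1. **SAP 4.7:** apply the 80–120% rule to the double-blind period only, and report run-in compliance separately.
2. **SAP 7.1:** restore the missing category, state that the analysis-set N is the denominator for the compliance categories, and reconcile 5.1 with 13.2.5.2.
3. **Missing return counts:** calculate compliance over the intervals that have both counts and flag the patient. Repeat the Evaluable analyses without patients whose compliance cannot be established, and define that status in advance (for example, no double-blind interval with both counts).
4. **Doses or tablets:** reconcile Protocol 3.5.5 with 5.6 and state which unit applies.
5. **SAP Section 11:** list these changes, together with the move of the compliance table from the ITT Population (Protocol 5.6) to the Safety Population (SAP 7.1).

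The cost is SAP wording and programming on counts already collected. The Evaluable Population may change by a few patients, and reported compliance may look slightly less favourable.

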### 7.2. Adverse Events

AEs will be coded using the MedDRA Version 20.0 or later and will be classified by MedDRA SOC and PT.

AEs are collected from date of signed informed consent form (ICF) through the last Follow-up Visit. TEAEs, SAEs, and on-therapy SAEs are defined in [Section 5.2.4](#). Pre-treatment AEs during Screening are defined as AEs started on/after Screening Visit and before the first dose of Run-in placebo. Pre-treatment AEs during Single-blind Run-in Period are defined as AEs started on/after the first dose of Run-in placebo and before the first dose of randomized study drug.

The number and percentage of participants who experience at least 1 TEAE as well as those who experience each specific SOC and PT will be presented by treatment group for the Safety Population. For presentation of AE incidence, AEs will be sorted by SOC, and within each SOC, by PT in the decreasing incidence of the last column of summary table, and then the column before it one by one. AEs will also be presented by severity (CTCAE v.4.03; Grade 1–Grade 5). For AEs that change severity ratings, the AE will be included only once in the summaries, under the maximum severity rating assigned by the Investigator. Additionally, TEAEs and SAEs occurring in the first, second, and fifth week of the double-

This document is confidential.

blind Treatment Period will be listed separately to distinguish among any effects of the initial dose (Week 1), the up-titrated dose (Week 2), and the further up-titrated dose (Week 5).

AEs occurring during Screening and the Single-blind Run-in Period will be summarized and listed separately.

More specifically, the following summary tables will be provided:

1. Overall Summary of TEAEs
2. Incidence of TEAEs by SOC and PT
3. Incidence of TEAEs by SOC, PT, and severity
4. Incidence of TEAEs by SOC, PT and relationship to double-blind study drug
5. Incidence of on-therapy SAEs by PT
6. Incidence of AEs leading to study drug discontinuation by PT
7. Incidence of pre-treatment AEs during Screening by SOC and PT (Screened Population)
8. Incidence of pre-treatment AEs during Single-blind Run-in Period by SOC and PT (Single-blind Run-in Population)
9. Incidence of adverse events of special interest (AESIs) by PT
10. Incidence of TEAEs by SOC, PT, and region (US vs. Lebanon)
11. Incidence of VOCs by PT
12. Summary of VOC events by location (eg, extremity) and outcome (eg, acute chest syndrome)

All AEs will be listed. In addition, list of all TEAEs and TEAEs occurring during the first, second, and fifth week of double-blind treatment period will be provided. Severe TEAEs (Grade  $\geq 3$  per CTCAE v.4.03 criteria), study drug-related TEAEs (those that are determined by the Investigator to be related to study treatment), SAEs, TEAEs leading to study drug discontinuation, AEs leading to death (if any), and AESIs will be presented in separate listings.

